2.7.4.2 Cardiovascular risk factor assessment

At the screening/baseline and at the end of treatment, for each subject information of the following risk factors is collected: smoking, low physical activity, unhealthy diet, and other. A listing will be presented.

Family medical history of each subject for ischemic heart disease, cardiac arrhythmia, sudden death, high cholesterol, diabetes mellitus, heart defects (congenital heart disease), and heart failure is also collected at the screening visit. A listing will be presented.

2.7.4.3 Vital signs

Vital sign assessments are performed in order to characterize basic body function. The following parameters were collected: height (cm), weight (kg), body temperature ($^{\circ}\text{C}$), heart rate (beats per minute), systolic and diastolic blood pressure (mmHg).

Data handling

Vital signs collected on treatment will be summarized. Values measured outside of on treatment period will be flagged in the listings.

Data analysis

The number and percentage of subjects with notable vital sign values (high/low) in systolic blood pressure, diastolic blood pressure, pulse rate, weight and temperature will be presented.

A listing of all vital sign assessments will be produced and notable values will be flagged. In the listing, the assessments collected outside of on-treatment period will be flagged.

2.7.4.4 ECOG performance status

ECOG performance status collected on treatment will be summarized. Shift tables will be provided comparing baseline with best and worst values during study.

2.8 Pharmacokinetic endpoints

Not applicable.

2.9 PD and PK/PD analyses

Not Applicable.

2.10 Patient-reported outcomes

The patient reported outcomes (PRO) objectives are to compare the impact of treatment on PROs including CML-specific symptoms and health related patient quality of life from baseline through end of treatment in all subjects by using FAS except stated otherwise. The M.D. Anderson Symptom Inventory – Chronic Myeloid Leukemia (MDASI-CML) questionnaire is planned to be administered during screening, at weeks 4, 12, 24, 48, 72, 96, 120 and end of treatment.

The MDASI-CML is a 26 item self-administered questionnaire for adult CML patients. Twenty of the items measure the severity of disease-related symptoms and are scored from 0 (Not present) to 10 (As bad as you can imagine) and 6 items that measure symptom interference with daily life scored from 0 (Did not interfere) to 10 (Interfered completely).

The severity score will be calculated when a subject scores at least 11 items out of the 20 severity items using the formula: (sum of scores for the items answered) / (number of items answered). If a subject scores fewer than 11 items, the severity score will be missing.

The interference score will be calculated when a subject scores at least 4 items out of the 6 interference items using the formula: (sum of scores for the items answered) / (number of items answered). If a subject scores fewer than 4 items, the interference score will be missing.

For the severity score and interference score, descriptive statistics (n, mean, SD, median, 25th and 75th percentiles) will be provided for the actual scores and changes from baseline scores at each scheduled assessment time point.

Subjects with an evaluable baseline score and at least one evaluable post baseline score during the treatment period will be included in the change from baseline analyses. Missing data items in a scale will be handled according to the manual for each instrument. No imputation will be applied if the total or subscale scores are missing at a visit.

The additional subjects who were intolerant to the last TKI and were in MMR already at baseline will be assessed for the change in PRO from baseline by using FAS 2.

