The reference start date for safety assessments (e.g. adverse event onset, laboratory abnormality occurrence, vital sign measurement, dose interruption, etc.) is the start of study treatment.

The reference start date for all other, non-safety assessments (e.g. molecular response, disease progression, ECOG performance status, patient reported outcomes (PRO), etc.) is the date of randomization.

The reference start date for dose escalation (200 mg q.d.) is the date when a subject starts first escalated dose.

The study day will be displayed in the data listings. If an event starts before the reference start date, the study day displayed on the listing will be negative.

Time unit

A year length is defined as 365.25 days. A month length is 30.4375 (=365.25/12) days. If duration is reported in months, duration in days will be divided by 30.4375. If duration is reported in years, duration in days will be divided by 365.25.

A week length is defined as 7 days. If duration is reported in weeks, duration in days will be divided by 7.

Baseline for the treatment period

For efficacy evaluations, the last non-missing assessment, including unscheduled assessments on or before the date of randomization is taken as “baseline” value or “baseline” assessment. In the context of baseline definition, the efficacy evaluations also include PRO and performance status.

For safety evaluations, the last available assessment, including unscheduled assessments before the date of start of study treatment is taken as “baseline” assessment.

For pre-dose electrocardiogram (ECG), the last available assessment before the treatment start date is used for baseline.

For ECGs requiring triplicate measures per time point, the average of these measurements will be reported by sites in eCRF baseline.

For mutations, the screening/baseline assessment is taken as “baseline” assessment.

In rare cases where multiple laboratory measurements meet the baseline definition, with no further flag or label that can identify the chronological order, then the following rule should be applied: If values are from central and local laboratories, the value from central assessment should be considered as baseline.

If subjects have no value as defined above, the baseline result will be missing.

On-treatment assessment/event and observation periods

For adverse event reporting the overall observation period will be divided into three mutually exclusive segments:

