1. ***pre-treatment period:*** from day of subject’s informed consent to the day before first administration of study treatment
2. ***on-treatment period:*** from date of first administration of study treatment to 30 days after date of last administration of study treatment (including start and stop date).
3. ***post-treatment period:*** starting at day 31 after last administration of study treatment.

If dates are incomplete in a way that clear assignment to pre-, on-, post-treatment period cannot be made, then the respective data will be assigned to the on-treatment period.

Safety summaries (tables, figures) on the corresponding Safety set include only data from the on-treatment period with the exception of baseline data which will also be summarized where appropriate (e.g. change from baseline summaries). In particular, summary tables for adverse events (AEs) will summarize only on-treatment events, with a start date during the on-treatment period. In addition, a separate summary for death will be provided.

However, all safety data (including those from the pre-treatment and post-treatment) will be listed and flagged as appropriate.

Efficacy summaries on the FAS and FAS 2 (apart from OS and PFS) include data from baseline up to either the last assessment on or before the End of Treatment (EoT) visit or before or on treatment failure, whichever is the earliest.

The efficacy assessments collected post-treatment failure or post-EoT visit are not included in any efficacy analyses (except for OS and PFS analyses). However, they will be listed and flagged as appropriate.

Windows for multiple assessments

Data such as molecular response, cytogenetic response collected over time (including unscheduled visits) will be summarized by scheduled time point. As subjects do not always adhere to the visit schedule, visits will be remapped according to visit windows defined in Tables 2-1 to Table 2-3 of this document to enable by-visit analysis. Only those protocol-defined visits will have the visit window defined. Each assessment (including the end of treatment assessment), either scheduled or unscheduled, will have a mapped visit assigned, as long as study day is available, according to the defined visit window up to the date with data included.

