2.2 Analysis sets

The subject population for the study includes subjects resistant or intolerant to 2 or more prior TKI treatments without MMR at baseline, and an additional group of subjects who were intolerant to the last TKI and were in MMR at baseline. Note that the YR data domain from IRT will be used to identify the stratification groups for the study population, and the biomarker data (B1 domain) containing BCR::ABL ratio will be used to confirm the MMR status at baseline for all subjects. If there is discrepancy between YR and B1 data, the MMR status at baseline will be assessed based on the B1 data.

The Analysis Sets are stated as follows:

Full Analysis Set

The Full Analysis Set (FAS) comprises all participants to whom study treatment has been assigned by randomization except the additional subjects who were intolerant to the last TKI and were in MMR at baseline.

Full Analysis Set 2

The Full Analysis Set 2 (FAS 2) comprises only the additional subjects who were intolerant to the last TKI and were in MMR at baseline and to whom study treatment has been assigned by randomization.

Safety Set

The Safety Set (SAF) includes all participants who received at least one dose of study treatment except the additional subjects who were intolerant to the last TKI and were in MMR at baseline.

Safety Set 2

The Safety Set 2 (SAF 2) includes only the additional subjects who were intolerant to the last TKI and achieved were in MMR at baseline and who received at least one dose of study treatment.

Unless otherwise stated, the analysis sets will be applied as below:

- For the subjects resistant or intolerant to 2 or more prior TKI treatments without MMR at inclusion to the trial
 - The FAS will be used for demographics and baseline characteristics (except disease characteristics) and all efficacy analyses including PROs
 - The SAF will be used for baseline disease characteristics, exposure and all safety analyses
- For the additional subjects who were intolerant to the last TKI and were in MMR at baseline
 - The FAS 2 will be used for demographics and baseline characteristics (except disease characteristics) and selected efficacy analyses including PROs
 - The SAF 2 will be used for baseline disease characteristics, exposure and selected safety analyses

Withdrawal of Informed Consent

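### SAP 2.1.1 read with SAP 2.2 would exclude on-treatment MDASI-CML scores after treatment failure, which contradicts SAP 2.10 and the protocol, where these scores are analysed through end of treatment

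*SAP*

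**What the plan says.** - **SAP 2.10** sets the PRO objective "from baseline through end of treatment in all subjects by using FAS". To enter the change analysis a subject needs a usable baseline value; the condition on later scores reads: "at least one evaluable post baseline score during the treatment period will be included in the change from baseline analyses". Nothing is said about treatment failure. On missing scores it adds: "No imputation will be applied if the total or subscale scores are missing at a visit".
- **SAP 2.1.1** (observation periods) ends efficacy summaries on FAS and FAS 2, apart from OS and PFS, at the last assessment up to the EoT "visit or before or on treatment failure, whichever is the earliest". It then states: "The efficacy assessments collected post-treatment failure or post-EoT visit are not included in any efficacy analyses (except for OS and PFS analyses"). PROs are not named as an exception.
- **SAP 2.2** assigns the FAS to "all efficacy analyses including PROs", and FAS 2 to a selection of efficacy analyses that again includes PROs.
- **SAP 5.4.4** defines failure as BCR::ABL1 above 1% or no CCyR at 48 weeks, a new T315I mutation, loss of response (including confirmed loss of MMR), or progression to AP/BC.
- **Protocol 9.1.1 and SAP 5.4.4** let a failing patient without alternatives continue on study drug if the investigator sees benefit. Patients above 10% after 48 weeks, or with signs of AP/BC, must stop.
- **Protocol 8.5.1 and 12.5.4** run the PRO analysis from baseline to end of treatment with no cut at failure. **SAP section 4** lists no change to protocol analyses.

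**The concern.** Change in symptom burden and interference over time is a listed secondary endpoint, and the SAP supports two different data sets for it. A programmer who follows 2.1.1 and 2.2 cuts each patient's MDASI-CML series at failure. One who follows 2.10 keeps it to the EOT visit. The two give different tables from Week 72 onward.

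Under the cut, the subjects removed are chosen by their molecular or cytogenetic result while they are still taking asciminib and still completing questionnaires. With no imputation they simply leave the later means, so a movement between Week 48 and Week 72 would mix change within patients with a change in who is counted.

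Part of the dose-escalation experience would go too. Confirmed loss of MMR is a failure event in SAP 5.4.4 and also a route to 200 mg q.d. in Protocol 6.1 and 6.6.2. Patients escalated by that route, and Week 48 failures who continue and escalate, would lose their post-escalation scores. Patients who escalate only because they are not in MMR at Week 48, with BCR::ABL1 at or below 1%, in CCyR and with no other failure event, would not.

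**Working it through.** **Plan's own figure.** The PRO analysis is descriptive and has none. The only design figure, 156 patients for 80% power (23% against 33%, exact test, one-sided 0.025), reproduces: rejection at 47 or more responders, exact alpha 0.0241, power 0.8010. It does not depend on this point.

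**The rules side by side, for a patient failing on BCR::ABL1 at Week 48 who stays on drug**

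| Scheduled questionnaire | SAP 2.1.1 with 2.2 | SAP 2.10; Protocol 8.5.1, 12.5.4 |
|---|---|---|
| Baseline, Weeks 4, 12, 24 | used | used |
| Week 48 (target day 337) | normally used | used |
| Week 72 (day 505), 96, 120, EOT | excluded | used |

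The Week 48 score normally stays because SAP 2.1.1 keeps assessments dated on the day of failure, and the Week 48 PCR and questionnaire belong to the same visit. A patient who fails on another criterion loses scores from that date, which may fall before or after Week 48. A patient who stops at failure has no later on-treatment visits under either reading, but an EOT questionnaire dated after the failure would be lost under the cut.

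**Illustration of size.** The documents do not give the inputs below, so all are assumptions:
- f, the share failing: 10% to 50%
- s, the share of failures staying on drug: 25% to 100%
- D, the amount by which failures score worse than non-failures: 0.5 to 2 points on the 0–10 scale
- all 156 subjects are on treatment at Week 48, and every non-failure stays on

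Share of on-drug subjects removed by the cut: w = f·s / (f·s + 1 − f). Shift in a later mean due to the cut = w × D.

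| f | s | Failures on drug (156·f·s) | Non-failures (156·(1−f)) | w | Shift at D = 1 |
|---|---|---|---|---|---|
| 10% | 25% | 3.9 | 140.4 | 3.9/144.3 = 0.03 | 0.03 |
| 30% | 50% | 23.4 | 109.2 | 23.4/132.6 = 0.18 | 0.18 |
| 50% | 100% | 78 | 78 | 78/156 = 0.50 | 0.50 |

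Across the full ranges the shift runs from 0.01 (w = 0.027, D = 0.5) to 1.0 points (w = 0.50, D = 2).

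**Separating the cut from ordinary dropout (middle row, D = 1).** At Week 48 the mean over everyone lies f × D = 0.30 points above the non-failure mean. At Week 72 under the cut only non-failures remain, so the mean falls by 0.30 with no patient changing. Without the cut it would still lie 0.18 above the non-failure mean. So 0.18 of the fall comes from the cut, and 0.30 − 0.18 = 0.12 from failures who left treatment, which happens under either reading.

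For change from baseline the formula is the same, but D becomes the gap in change, which need not equal the gap in level.

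**The case against.** The strongest reply is that no sentence in the SAP says PRO scores are cut at failure. The exclusion comes from joining a general rule to a phrase that assigns analysis sets, and several places suggest a narrower sense of efficacy:
- SAP 2.1.1 says "In the context of baseline definition, the efficacy evaluations also include PRO and performance status". That qualifier would be unnecessary if PROs were efficacy evaluations throughout.
- Table 2-4 glosses efficacy assessments as molecular or cytogenetic.
- SAP 5.5.1 splits missing data by failure status only for those two responses.
- Protocol 8.3 covers molecular, cytogenetic and hematologic response, while PROs sit under 8.5.

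On this view the specific section, 2.10, governs.

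That argument stands against the stronger reading that the SAP plainly drops these scores. It does not remove the conflict. SAP 2.1.1 covers all efficacy summaries on FAS and FAS 2 and names its exceptions; SAP 2.2 puts PROs among the efficacy analyses for both sets. The allowance in 2.10 for statements elsewhere follows the mention of the FAS and most naturally concerns the analysis set. A reader cannot tell which rule wins.

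Other points also stand. A reader might infer that the Week 48 mean already covers only non-failures; it does not, because failure-date scores are kept. A reader might infer a known bias in asciminib's favour; the documents give neither the share of failures on drug nor their scores, so even the sign is open. Continuing after failure is an exception to the general rule of stopping. SAP 2.10 already reports n at each time point, so a drop would be visible, and excluded efficacy assessments would still be listed and flagged. The endpoint is descriptive in a non-comparative study.

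**Conclusion.** The point holds as an unresolved contradiction in the SAP about a listed secondary endpoint. SAP 2.1.1 with 2.2 excludes on-treatment MDASI-CML scores after failure; SAP 2.10 and Protocol 8.5.1 and 12.5.4 include them; section 4 declares no departure. If the cut were applied, later PRO means would be selected on response, normally from Week 72 for Week 48 failures.

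The size cannot be fixed from the documents. The 0.03 to 0.50 points at a 1-point gap rest wholly on assumed failure and continuation shares and on failures scoring worse; if they scored better, the shift would reverse. The group could be wide, since SAP 5.4.2 counts missing cytogenetics as non-response unless the subject is in MMR. At the design alternative, 156 × (1 − 0.33) ≈ 105 subjects would not be in MMR, but how many of them would meet a failure criterion is not stated.

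The primary endpoint, sample size and power are unaffected. This should be corrected, but it does not threaten the trial's main conclusion.

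**What to change.** - **SAP 2.1.1:** add PROs to the exceptions beside OS and PFS, or limit the post-failure exclusion to molecular and cytogenetic response analyses.
- **SAP 2.10:** state that all MDASI-CML assessments up to the EOT visit are used regardless of treatment failure, for both FAS and FAS 2.
- **Optional:** show n by failure status at each visit, so that readers can see how the group changes. This goes beyond the overall n already planned.

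If the sponsor does intend the cut, 2.10 should say so and SAP section 4 should record the departure from the protocol.

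The cost is a sentence or two in each section. The questionnaires are already scheduled and collected, so there is no new data collection and no effect on sample size.

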2.11 Biomarkers

CCI

CCI

CCI

CCI

2.12 Other Exploratory analyses

Not applicable.

2.13 Interim analysis

No formal interim analysis is planned for this trial. The following analyses are planned as detailed below.

- 48-week primary analysis: Formal testing of the primary endpoint will be performed. Analyses of other efficacy endpoints at and by week 48 and safety analyses will also be performed.
- 96-week analysis: Analyses of efficacy endpoints at and by week 96 and safety analyses will be performed.
- End of study treatment analysis similar to the 96-week analysis without formal statistical testing. All efficacy and safety analyses will be included.

3 Sample size calculation

A sample size of 156 subjects (randomized to either asciminib 40 mg b.i.d. or 80 mg q.d.) will have 80% power to reject the null hypothesis proportion of 23% (upper limit of 95% exact binomial CI of the MMR rate at Week 48 in Bosutinib arm in ASCEMBL: see below) at 0.025 one-sided level of significance if the true rate (under alternative hypothesis) is 33% (considering a clinically meaningful difference of 10% or more) using exact test for single proportion (nQuery 7).

The MMR rate (95% CI) at Week 48 in Bosutinib arm of ASCEMBL trial (at ASCEMBL study Week 24 primary CSR (Data cut-off date of 25-May-2020, Table 14.2-1.1.1)) was 11.1 % (4.2% – 22.6%); 54 subjects were eligible for this sample size computation.

An additional 30 subjects based on medical justification (randomized to either asciminib 40 mg b.i.d. or 80 mg q.d.) intolerant only to last TKI and in MMR at baseline will also be analyzed.

4 Change to protocol specified analyses

Not applicable.

5 Appendix

5.1 Imputation rules

5.1.1 Study drug

The following rules should be used for the imputation of the dose end date for a given study treatment component.

Scenario 1: If the dose end date is completely missing and there is no EOT page and no death date, the subject is considered as on-going:

The subject should be treated as on-going and the cut-off date should be used as the dose end date.

Scenario 2: If the dose end date is completely missing and the EOT page is available:

The EOT completion date should be used.

- All other cases should be considered as a data issue and the statistician should contact the data manager of the study.
- After imputation, compare the imputed date with start date of treatment, if the imputed date is < start date of treatment:

Use the treatment start date

Subjects with missing start dates are to be considered missing for all study treatment component related calculations and no imputation will be made. If start date is missing then end-date should not be imputed.

5.1.2 AE, ConMeds and safety assessment date imputation

The imputations specified in this section are only used for analyses of time to and duration of AEs and concomitant medications.

Table 5-1 Imputation of start dates (AE, CM) and assessments (eg: LB, EG, VS)

Missing Element	Rule
day, month, and year	
 No imputation will be done for completely missing dates
day, month	
 If available year = year of study treatment start date then 
 If stop date contains a full date and stop date is earlier than study treatment start date then set start date = 01JanYYYY Else set start date = study treatment start date. If available year > year of study treatment start date then 01JanYYYY If available year < year of study treatment start date then 01JulYYYY
day	
 If available month and year = month and year of study treatment start date then 
 If stop date contains a full date and stop date is earlier than study treatment start date then set start date= 01MONYYYY. Else set start date = study treatment start date. If available month and year > month and year of study treatment start date then 01MONYYYY If available month and year < month year of study treatment start date then 15MONYYYY

Table 5-2 Imputation of end dates (AE, CM) and assessments (eg: LB, EG, VS)

Missing Element	Rule (* = last treatment date plus 30 days not > (death date, cut-off date, withdrawal of consent date))
day, month, and year	
 Completely missing end dates (incl. ongoing events) will be imputed by the end date of the on-treatment period*
day, month	
 If partial end date contains year only, set end date = earliest of 31DecYYYY or end date of the on-treatment period *
day	
 If partial end date contains month and year, set end date = earliest of last day of the month or end date of the on-treatment period*

Any AEs, ConMeds or assessments with partial/missing dates will be displayed as such in the data listings.

Any AEs, ConMeds or assessments which are continuing as per data cut-off will be shown as 'ongoing' rather than the end date provided.

